5.6 CONFIDENTIALITY AND SECURITY OF DATA

Secure storage: Data will be housed in a HIPAA-compliant secure storage system, like REDCap or Box, within the Cedars-Sinai network with access restricted to approved members of the research team.

Limited Access: Private identifiable information, will be accessible only to IRB approved study team members with current IRB training.

Unique ID Numbers: Each patient will be assigned a unique ID number.

Removal of Identifiers: Direct identifiers (like name or MRN) will be removed from the research records and destroyed as soon as scientifically possible and maintained only as long as necessary to abstract, analyze and verify data.

6.0 DATA AND SAFETY MONITORING

6.1 DATA AND SAFETY MONITORING PLAN

A data safety and monitoring plan will be used to ensure subject safety and data integrity. Any adverse event that may be harmful to a subject taking part in the study will be reported on the appropriate case report form. If the investigators are unsure about whether to report an occurrence as an adverse event, they are to contact the study's medical monitor. Adverse events will be assessed from the time of the start of the index surgery (first incision) and at all follow-up visits and will include a brief description of the event as well as the duration and the outcome. An event is considered a serious adverse event if it results in death or leads to serious deterioration of the health of the subject. Unanticipated adverse device effect will be defined as any serious adverse effect on health or safety caused by or associated with a device or software program. Both of these types of adverse events will be reported to the IRB within 24 hours.

6.2 QUALITY CONTROL AND QUALITY ASSURANCE

The clinical monitor will verify that appropriate data is recorded for all study subjects for whom informed consent is obtained; and that no study specific procedures or treatments are administered without informed consent.

7.0 STATISTICAL CONSIDERATIONS

7.1 STUDY OUTCOME MEASURES

- Primary Outcome analysis: 2 tailed T-test for average length of surgery (skin to skin), average time to place 2 interlocks (start time when nail is seated and surgeon states s/he is ready to proceed with distal interlocking screw placement). Average radiation used in microGrays. Femur vs tibia average time to place 2 interlocks and average radiation exposure.
 - To compare time and accuracy of placement only data from surgeons who have performed both DT and FH techniques more than 5 times will be included.
- Secondary outcomes: t-test accuracy of screw placement (perpendicular to nail)
 - Multivariate regression evaluating predictors of time to placement
 - Level of training
 - Number of cases performed
 - Number of interlocking screws placed
 - Time since last case
 - Learning curve assessment
 - Time of each interlocking screw placement will be correlated with number of interlocking screws placed
 - Time of procedure and accuracy of placement will be analyzed in increments of 5 cases to evaluate for number of cases required to reach plateau
 - Data will be stratified by level of training

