2.0 STUDY OBJECTIVES

Outcomes:

- Primary outcomes: radiation exposure, time, accuracy of placement (right angle to rod).
 - Each distal interlock will be considered a separate outcome
 - The first fluoroscopy shot to localize the jig or obtain a perfect circle is considered start time. The surgeon will note the hour, minute, and seconds of the time based on the wall clock in the operating room.
 - The last shot to confirm complete seating of the screw will be considered end time. The surgeon will note the hour, minute, and seconds of the time based on the wall clock in the operating room.
- Secondary outcomes:
 - accuracy of placement (right angle to intramedullary nail).
 - Number of complete misses of the nail with the drill or the screw
 - comparison of learning curve between distal targeter and freehand techniques stratified by level of training
 - The level of training of the surgeon
 - Experience level of the surgeon
 - estimated number total number of intramedullary nails placed
 - time since the last intramedullary nail placement
 - estimated number of nails placed per month over the last year
 - number of times the surgeon has used the distal targeting system
 - Comparison of tibia vs femur antegrade nails

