3.5 SUBJECT RECRUITMENT

Patients will be recruited from all full-time orthopaedic trauma faculty. The treating surgeon and/or clinical research associate will approach patients in person to recruit, enroll and consent them for the study. No advertisement will be used for this study.

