4.0 STUDY DESIGN AND METHODS

This study will be a prospective, randomized control trial. Patients will be randomized to perform distal interlock screen insertion either by freehand or distal targeting for all lower extremity nails.

1. All patients undergoing femoral or tibial nailing will undergo one method of interlock placement starting on the first of the month starting with free-hand locking. The method of interlocking screw placement will then switch to jig-based screw placement at the first of the following month. The method of screw placement will alternate each week until enrollment is complete. This method of enrollment for clinical modalities that are already in common use has previously been described with the PREP-IT trials. [Slobogean et al, JAMA Netw Open 2020]
2. Due to the nature of the distal targeting jig's construction, there may be instances where its use is not possible due to interference with other surgical instrumentation, and an intraoperative decision must be made to place screws with the freehand technique. Patients randomized to the jig-based placement arm but are ultimately treated with freehand placement will be documented and reported as crossover patients (per the CONSORT framework).
3. Patients randomized to their respective groups will ultimately undergo intention-to-treat analysis.

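### The primary t-tests have no operator term, although the plan names operator experience as a predictor of placement time and nothing keeps the choice of operator independent of a technique known in advance.

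*Combined protocol and SAP*

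**What the plan says.** Section 7.1 specifies "Primary Outcome analysis: 2 tailed T-test for average length of surgery (skin to skin), average time to place 2 interlocks", then average radiation. Accuracy also gets a t-test, listed there as secondary, while section 2.0 lists accuracy under both primary and secondary outcomes. No operator term or stratum appears in any of these tests.

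Operators are expected to differ. Section 3.5 states: "Patients will be recruited from all full-time orthopaedic trauma faculty". Section 2.0 lists the surgeon's level of training, total nails placed, nails per month, time since the last nail and prior uses of the targeting system. It also plans a "comparison of learning curve between distal targeter and freehand techniques stratified by level of training".

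Two provisions in 7.1 touch on operators. One restricts the data that enter the comparison: "To compare time and accuracy of placement only data from surgeons who have performed both DT and FH techniques more than 5 times will be". The other is a secondary "Multivariate regression evaluating predictors of time to placement", whose listed predictors are level of training, cases performed, screws placed and time since the last case. Technique is not on that list.

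On allocation, section 4.0 says that patients "will undergo one method of interlock placement starting on the first of the month starting with free-hand locking", and then: "The method of interlocking screw placement will then switch to jig-based screw placement at the first of the following month". The next sentence reads: "The method of screw placement will alternate each week until enrollment is complete". Section 4.0 has no rule on who places the screws. The variable list in 5.3 has no field for operator identity, training or nail count.

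**The concern.** An unadjusted two-sample comparison isolates technique only if the people placing the screws are comparable in the two arms. Here the plan itself expects operator experience to drive placement time. The technique in force is public before the case, and the choice of operator is left open. If the mix of operators differs between arms, for whatever reason, part of that difference enters the estimated technique effect on time, radiation or accuracy. It could exaggerate the jig's benefit or hide it.

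There is a second cost even when the mix is similar. Leaving out a strong predictor leaves its variance in the error term. The regression that contains the operator variables cannot repair either problem, because as listed it estimates no technique effect.

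**Working it through.** **The plan's own figure.** Section 7.2 gives means of 616 s and 344 s, SD 192 s, 90% power and 5% significance; 7.1 makes the test two-tailed.

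- Difference: 616 − 344 = 272 s, and 272/616 = 44%, as stated.
- n per technique arm = 2 × (1.960 + 1.282)² × 192²/272² = 10.5, so 11, or 22 per cohort.
- Dividing by the 75% participation rate: 22/0.75 = 29.3, so 30 per cohort.
- Two cohorts (tibia and femur) make 60, and 60/0.91 = 65.9, so 66.

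The figures reproduce. Assuming 1:1 allocation, 30 per cohort means 15 per technique arm within a cohort, or 30 per arm with the cohorts pooled. Both sizes are used below.

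**Bias from operator mix.** Bias = (difference between arms in the share of slower operators) × (slower minus faster operator time). The documents give neither input, so both are assumptions.

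- 0.20 × 100 = 20 s, and 20/272 = 7%.
- 0.20 × 300 = 60 s, and 60/272 = 22%.
- 0.30 × 100 = 30 s, and 30/272 = 11%.
- 0.30 × 300 = 90 s, and 90/272 = 33%.

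**False-positive rate of the plain t-test when technique has no effect.** Let g be the gap and m the difference in mix, with shares p = 0.5 ± m/2 and within-operator SD 192 s. The variance in each arm is 192² + g²p(1 − p). The rejection rate comes from the noncentral t distribution with 2n − 2 degrees of freedom.

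Worked case: g = 192 s, m = 0.40. The variance is 36,864 + 36,864 × 0.21 = 44,605. At 15 per arm, SE = √(2 × 44,605/15) = 77.1 s against a bias of 76.8 s. At 30 per arm, SE = 54.5 s.

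| Gap (s) | Difference in mix (points) | Bias (s) | Share of 272 s | False positive, 15 per arm | False positive, 30 per arm |
|---|---|---|---|---|---|
| 96 | 20 | 19 | 7% | 5.8% | 6.6% |
| 192 | 20 | 38 | 14% | 7.6% | 10.5% |
| 192 | 40 | 77 | 28% | 16.1% | 28.3% |
| 272 | 60 | 163 | 60% | 49.8% | 80.4% |

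The nominal rate is 5%. The last row is an extreme.

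**Effect of an operator term.** A linear model with a two-level operator variable was simulated for gaps of 96 and 192 s and mix differences of 20, 40 and 60 points. There were 10,000 runs per setting, with operator counts fixed in each arm.

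- In the 192 s, 40-point case, the false-positive rate fell from 12.9% to 4.9% at 15 per arm, and from 26.0% to 5.2% at 30 per arm. The unadjusted rates differ a little from the table because the counts are fixed.
- With a true 272 s reduction and the slower operators concentrated in the jig arm, the unadjusted estimate averaged 196 s. Power at 15 per arm was 70% unadjusted and 93% adjusted.
- Across all simulated settings, the adjusted model held type I error at 4.6% to 5.2%. Power was about 85% to 96% at 15 per arm and about 99% or more at 30 per arm.

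The simulated model is correctly specified, so it shows what adjustment does for measured operator differences only.

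**The case against.** Several points against this concern have force.

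- **Operator selection is not in the documents.** A reader might infer that faculty will hand one technique to trainees and keep the other. Nothing says so. It is a possibility left open by a missing rule.
- **The blocks need not be few.** A reader might infer that long calendar blocks will coincide with trainee rotations. That rests on the monthly sentences alone. The weekly sentence, over the roughly one year in 5.2, would give dozens of blocks, and any rotation longer than two weeks would span both techniques. Section 4.0 contradicts itself on this and must be reconciled. Case-by-case choice of operator remains open on either reading.
- **The plan is not silent on skill.** Requiring more than 5 uses of both techniques excludes novices and ensures that each included operator has used both. It still does not equalise how many cases each operator contributes to each arm. It names time and accuracy, not radiation.
- **The illustrated bias is modest.** The smallest significant difference at SD 192 s is about 144 s at 15 per arm and 99 s at 30 per arm, so 20 to 90 s would not usually reach significance alone. The 300 s gap is generous. If the 192 s SD already includes operators mixed 50:50, that gap would account for (150/192)² = 61% of the variance.
- **Operator may be a post-assignment variable.** If technique influences who operates, adjustment no longer estimates the total effect of assignment, and the documents do not state that equal operator skill is the target. This is largely met by adjusting for traits the operator brings to the case, attributing each screw to the person who starts it, and keeping the t-test as supportive.

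Predictable calendar allocation is the root cause, and operator mix is one consequence of it. The missing operator-adjusted estimate is a separate gap in 7.1.

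**Conclusion.** The concern holds as a gap in the analysis plan. The primary contrast ignores predictors that the plan itself names, technique is known before the operator is settled, and no listed analysis estimates a technique effect adjusted for operator. The existing experience rule reduces the problem for time and accuracy without removing it.

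The documents do not establish that bias will occur, which way it would run, or how large it would be. The 20 to 90 s range (7% to 33% of 272 s) rests wholly on an assumed gap and an assumed difference in mix. The false-positive rates further assume a within-operator SD of 192 s, two operator levels and 1:1 allocation. It would be wrong to read them as forecasts, or to conclude that a 272 s effect would be explained away.

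The change is worth making in any case. If the mix differs, the model removes the measured part of the bias. If the mix is similar, it removes between-operator variance. It should be made before further enrolment, because operator details not recorded at surgery may not be recoverable.

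**What to change.** - **7.1, technique contrast:** estimate the technique effect on time, radiation and accuracy with a linear model of outcome on assigned technique, adjusted for the operator's level of training and prior nail count. Use a random intercept for surgeon, or standard errors that allow for surgeon. Avoid fixed surgeon effects, which would be nearly collinear with training level in about 60 patients. Keep the t-test as a supportive analysis.
- **7.1, secondary regression:** add assigned technique to the listed predictors.
- **5.3:** add an operator study code, level of training and prior nail count for the person who starts each screw, and a note of any takeover.
- **4.0:** state that the person placing the distal screws is set without reference to the technique in force. Reconcile the monthly and weekly sentences.

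The cost is a few degrees of freedom, a less simple headline analysis and a few form fields. No extra patients are needed. The degrees of freedom matter most within a single cohort, where the calculation leaves about 11 evaluable patients per arm, so the covariates should stay at the two named.

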7.2 SAMPLE SIZE CONSIDERATIONS

- Power: Based on a more recent paper from Konda et al, the average time for distal interlocking screw placement was 616 seconds in the control and 344 seconds in the distal targeting with an SD of 192 seconds. This suggests that a total of 30 patients would need to be enrolled for each cohort to detect a 44% decrease in the amount of time required for distal interlocking screw placement with the distal targeter with 90% power at 5% significance. (sealedenvelope.com power calculator on-line)
 - Estimating a 75% participation rate, we intend to enroll 60 patients (30 in each cohort – tibia and femur surgeries) that meet the sub-study criteria
 - Given that 9% of the currently enrolled patients (included in the main study) will not meet the sub-study criteria (retrograde nails instead of antegrade), we intend to enroll a total of 66 total patients for this study (includes patients for main study and sub study).

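### Technique is assigned by alternating calendar period, but 7.1 and 7.2 treat patients as independent: type I error is inflated if outcomes correlate within a period, slightly if weekly, materially if monthly

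*Combined protocol and SAP*

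**What the plan says.** Section 4.0 opens in individual-level language: "Patients will be randomized to perform distal interlock screen insertion either by freehand or distal targeting for all lower extremity nails". The procedure beneath it describes something else: "All patients undergoing femoral or tibial nailing will undergo one method of interlock placement starting on the first of the month starting with free-hand locking". A monthly switch follows, "The method of interlocking screw placement will then switch to jig-based screw placement at the first of the following month", and then a weekly one, "The method of screw placement will alternate each week until enrollment is complete". Everyone treated in a period is therefore allocated to the same technique, and free-hand leads the sequence.

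Section 7.1 plans "Primary Outcome analysis: 2 tailed T-test for average length of surgery (skin to skin), average time to place 2 interlocks". Radiation is listed under the same item, and accuracy has its own t-test as a secondary outcome. There is no period term, mixed model, robust standard error or period-level summary. The regression, "Multivariate regression evaluating predictors of time to placement", lists training and experience variables but neither technique nor period.

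Section 7.2 derives the sample size from two means and one SD, "with 90% power at 5% significance", with no allowance for period.

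**The concern.** A two-sample t-test on patients takes its standard error from the spread between patients, as if each had been allocated separately. When whole periods are allocated, anything that makes outcomes within a period alike adds variance to the difference between techniques, and the t-test does not count it. Confidence intervals are then too narrow, and the false-positive rate exceeds 5%.

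The comparisons affected are interlock time, length of surgery, radiation and accuracy between techniques. The femur-versus-tibia comparison in the same item of 7.1 is not affected in this way, because bone is not what the periods assign. The large time difference assumed in 7.2 is least at risk. Smaller effects, and analyses within one cohort, are most exposed.

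This point concerns the unit of analysis. Whether the sequence is random or concealed is a separate question.

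**Working it through.** **Inputs.** From 7.2: means 616 s and 344 s (difference 272 s), SD 192 s, 90% power, 5% two-sided (7.1 specifies two tails), 75% participation, 9% outside the sub-study, 66 patients in total. From 5.2: about 1 year. From 4.0: period of a week or a month. Assumed: ICC 0.05, 0.10 and 0.20.

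**Step 1: reproduce the plan's figure.** n per arm = 2 × (1.960 + 1.282)² × 192² / 272² = 10.47, rounded up to 11. That is 22 per cohort. 22 / 0.75 = 29.3, rounded up to 30. Two cohorts give 60, and 60 / 0.91 = 65.9, or 66. The plan's numbers follow, and the formula assumes independent patients.

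**Step 2: patients per period.** Weekly: m = 66 / 52 = 1.27. Monthly: m = 66 / 12 = 5.5.

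**Step 3: how far the standard error is understated.** With equal period sizes the design effect is 1 + (m − 1) × ICC. With sizes varying as Poisson counts it is 1 + m × ICC. The true standard error is the naive one times the square root. For Poisson sizes, the approximate type I error is 2 × [1 − Φ(1.96 / SE ratio)].

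| Period | ICC | Design effect, equal / Poisson | SE ratio (Poisson) | Approximate type I error | Simulated type I error |
|---|---|---|---|---|---|
| Weekly | 0.05 | 1.013 / 1.063 | 1.031 | 5.7% | 6.0% |
| Weekly | 0.10 | 1.027 / 1.127 | 1.062 | 6.5% | 6.7% |
| Weekly | 0.20 | 1.054 / 1.254 | 1.120 | 8.0% | 7.8% |
| Monthly | 0.05 | 1.225 / 1.275 | 1.129 | 8.3% | 8.0% |
| Monthly | 0.10 | 1.450 / 1.550 | 1.245 | 11.5% | 11.4% |
| Monthly | 0.20 | 1.900 / 2.100 | 1.449 | 17.6% | 18.5% |

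The last column comes from simulating the planned t-test with 66 patients placed at random over 52 or 12 alternating periods. Repeat simulations moved these figures by no more than about 1.5 percentage points. At ICC 0 the test runs at about 5% under either schedule.

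**Step 4: does a period-level analysis repair it?** In the same simulations, a t-test on period means held 4.5% to 5.7%.

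**Step 5: what that costs in power at 272 s (272 / 192 = 1.417 SD).** Pooled, 66 patients, period-mean test: 98%, 97% and 94% with monthly periods at ICC 0.05, 0.10 and 0.20, and over 99% with weekly periods. An analytic calculation with 60 patients and 12 − 2 = 10 degrees of freedom gives a minimum of about 93% for monthly periods. For one cohort of 30, the size that 7.2 sets, power is about 78% to 82% with monthly periods (a second simulation gave 83%, 81% and 76%) and about 92% with weekly periods.

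**Step 6: calendar trend.** Free-hand leads the sequence, so under regular alternation each jig period follows a free-hand one. A linear trend explaining 20% of the variance (assumed), with no period correlation, gave a type I error of 8.5% with monthly and 4.8% with weekly periods. This is bias, and a larger standard error alone does not remove it.

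**The case against.** The strongest reply is that the harm is conditional. The documents give no within-period correlation, and with none the planned t-test holds its level. A reader might infer from the design alone that every technique comparison has a standard error that is too small. The documents do not support that; they show only that the analysis has no protection if correlation exists.

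A reader might also assume that patients in a period share an on-call team, trainees and case mix. No section says so. Section 3.5 recruits from all full-time trauma faculty, and no call or rotation schedule is described. Nor does surgeon correlation by itself make the case: 7.1 limits the time and accuracy comparisons to surgeons experienced in both techniques, so surgeons are likely to contribute to both arms. A simulated surgeon share of 20% of the variance, with no period effect, left type I error at 5.2% to 5.3%. What does make some period correlation plausible is that 7.1 itself expects time to depend on experience, recency and a learning curve, all of which move with the calendar.

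Finally, the larger figures need monthly switching throughout, which the weekly sentence contradicts. Section 4.0 can also be read as one free-hand month, one jig month, then weekly alternation. That schedule gave 6.6%, 7.4% and 9.1% at the three ICCs. This stands, and it limits the weight of the point until the schedule is settled. It does not remove the mismatch between assignment and analysis.

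**Conclusion.** The mismatch is real: periods are assigned, patients are analysed and counted as independent, and no other section adds a period term. If outcomes correlate within a period, the technique tests are anti-conservative: about 6% to 8% type I error with weekly periods and about 8% to 18% with monthly periods. These figures assume ICC 0.05 to 0.20, all 66 patients analysed, and enrolment spread evenly by chance over a year.

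A reader might conclude that the trial is too small, or that no power is lost. Neither holds in general. The pooled comparison at 272 s is safe across the assumed range. The stated 90% for a single cohort of 30 may not hold under a period-level analysis with monthly switching.

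This should be fixed before analysis. Its weight depends on the period length: modest if weekly, substantial if monthly.

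**What to change.** 1. **Section 4.0:** reconcile the monthly switch with the weekly alternation, so that the unit of assignment is defined. The model below cannot be specified until this is done.
2. **Section 7.1:** replace the technique t-tests with a linear mixed model per outcome: technique fixed, calendar period random, small-sample degrees of freedom, adjusted for calendar date. The simple alternative is a t-test on period means, or, to include date, a regression of period means on technique and date. With weekly periods about half of the non-empty weeks would hold one patient, so the period variance will be poorly estimated and period means may be the steadier choice. If outcomes are analysed per screw, as 2.0 suggests, add a patient term.
3. **Section 7.2:** state that the calculation assumed independent, individually assigned patients, and that 90% power per cohort of 30 may not hold under monthly switching.

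The cost is SAP wording; date of surgery is already collected (5.3). Intervals will be wider. Over the assumed ICCs with Poisson period sizes, the standard error rises by 3% to 12% with weekly periods and by 13% to 45% with monthly periods, the latter with only about 10 degrees of freedom.

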3.3 EXCLUSION CRITERIA

- Prior ipsilateral tibial or femoral nail
- Patients who cannot have interlocking screws placed
- Pregnant patients
- For sub-study only: retrograde nails

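### Sections 2.0 and 7.1 give different start events for interlock time and different primary outcome lists, with no lead outcome or multiplicity rule

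*Combined protocol and SAP*

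**What the plan says.** **Start event.** Section 2.0, under the primary outcomes: "The first fluoroscopy shot to localize the jig or obtain a perfect circle is considered start time". Section 7.1, under the primary outcome analysis and attached to the average time for two interlocks: "start time when nail is seated and surgeon states s/he is ready to proceed with distal interlocking screw placement". An end event appears only in 2.0: "The last shot to confirm complete seating of the screw will be considered end time". That end event can serve both sections.

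**Primary list.** Section 2.0 has "Primary outcomes: radiation exposure, time, accuracy of placement (right angle to rod"), then lists "accuracy of placement (right angle to intramedullary nail") again among the secondary outcomes, together with "Comparison of tibia vs femur antegrade nails". Section 7.1 puts length of surgery, time for two interlocks, radiation, and a femur-versus-tibia entry for time and radiation under the primary analysis. It makes accuracy secondary.

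**Unit.** Section 2.0 adds "Each distal interlock will be considered a separate outcome". Section 7.1 averages over two interlocks for the primary and analyses individual screws in the learning curve.

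**Analysis set.** Section 4.0 states intention-to-treat. Section 7.1 limits time and accuracy, but not radiation, to surgeons who have used both techniques more than 5 times. Section 3.3 has "For sub-study only: retrograde nails".

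**Size and error.** Section 7.2 sizes interlock time alone, with 90% power at 5%. Neither it nor any other section names a lead outcome, a testing order, a split of alpha or an adjustment.

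**The concern.** A statistician following the plan would find two definitions of the only sized variable and two lists of primary outcomes. Any work between the surgeon declaring readiness and the first shot counts under 7.1 and not under 2.0. If the amount of that work differs between jig and freehand, the choice of clock changes the treatment contrast itself and does not merely add noise. The surgeon, who knows the method, also notes the 2.0 times.

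With several primaries, no lead outcome and no adjustment, a success on any one of them could be reported as a positive trial. Where both start times exist, the clock could also be settled after results by arm are known.

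**Working it through.** **1. The two sections side by side.**

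| Item | Section 2.0 | Section 7.1 |
|---|---|---|
| Start of interlock time | First fluoroscopy shot | Nail seated, surgeon declares readiness |
| Interlock time | Primary | Primary |
| Radiation | Primary | Primary |
| Accuracy | Primary and secondary | Secondary |
| Length of surgery | Not listed | Primary |
| Femur versus tibia | Secondary | Under the primary analysis |

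Only interlock time and radiation are primary in both. Section 5.3 does not settle the clock: its variable list has length of surgery and radiation but no interlock start or end time.

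**2. False-positive risk.** Section 2.0 names three primaries (radiation, time, accuracy). Section 7.1 also has three that compare jig with freehand (length of surgery, time, radiation). The only significance level stated is 5% (7.2), and 7.1 makes the tests two-tailed.

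- Independent tests: 1 − 0.95³ = 0.143, or 14.3%.
- Equicorrelated normal statistics, with assumed correlations: 13.6% at 0.3 and 10.9% at 0.7.

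**3. Reproducing 7.2.** Inputs from 7.2: means 616 s and 344 s, SD 192 s, 90% power, 5% level. Two-sided testing is from 7.1; 1:1 allocation is assumed.

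- Difference: 616 − 344 = 272 s; 272/616 = 44%.
- n per arm = 2 × (1.960 + 1.282)² × 192² / 272² = 10.5, rounded up to 11. Two arms make 22.
- 22 / 0.75 = 29.3, rounded up to 30 per cohort.
- Two cohorts, tibia and femur: 60. Then 60 / 0.91 = 65.9, rounded up to 66.

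So 30/60/66 reproduces when a cohort is a bone and the sizing is jig versus freehand within it. Read as 30 per treatment arm it does not reproduce, since only 11 per arm are needed.

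**4. Power by choice of primary.** Two-sample t-test, standardised effect 272/192 = 1.417. The 75% participation is read as loss from the 60, and clustering is ignored. Pooled: 60 × 0.75 = 45, about 22 per arm. One bone: 30 × 0.75 = 22.5, about 11 per arm.

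| Comparison | n per arm | Power at 5% | Power at 2.5% |
|---|---|---|---|
| Pooled over bones | 22 | 99.6% | 99.0% |
| Within one bone | 11 | 88.5% | 80.8% |

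The 2.5% column is the first Holm step for two tests. If the 60 already allow for refusals, the numbers become 30 and 15 per arm, and power at 5% is above 99.9% pooled and 96.3% within one bone.

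**5. Start event.** The documents give no duration for the interval between readiness and first shot in either arm. Its effect on the 272 s contrast cannot be computed.

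**The case against.** The best defence is that there are two clocks by design: a per-screw clock in 2.0, beside the statement that each interlock is a separate outcome, and a two-screw clock in 7.1, which analyses single screws separately in the learning curve. That is a possible intention. But no section says so, and both clocks sit under the primary time outcome, so the need to reconcile them stands. The same defence does work for the unit wording, which may only separate recording from analysis.

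Four stronger readings are tempting, and the documents do not support them.

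- *The start event will be picked after results are seen.* Only the first-shot start has a written recording instruction. If readiness times were never noted, there is no such choice to exploit.
- *The surgeon restriction contradicts intention-to-treat.* Section 4.0 makes that statement directly after describing crossovers, so it can be read as analysis by assigned method. If the more-than-5 count means experience before the trial, the two are compatible. The text does not say whether it means before or during.
- *The femur-versus-tibia entry adds two more primary tests and a higher error rate.* It could mean bone against bone, or jig versus freehand within each bone. The count is not determined, and one common correlation across technique and bone contrasts would be a poor model.
- *Nothing is said about retrograde nails.* Sections 3.3 and 7.2 keep them in the main study and out of the sub-study. What remains open is which of the two the sized time comparison belongs to.

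**Conclusion.** The point holds, and it should be settled before any comparison by arm. The start event differs between 2.0 and 7.1 for the only sized variable, the primary lists conflict on three items, one of them within 2.0 itself, and there is no error rule. These are findings on the text and need no assumption.

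The 14.3% (10.9% to 13.6% with correlation) is conditional on three primaries each tested at two-sided 5%; the correlations are assumed. The missing rule is a matter of error control more than of sample size: a pooled time comparison keeps about 99% power even at 2.5%. A by-bone comparison does not have that margin. The power figures rest on 7.2's means and SD, 1:1 allocation, no clustering by surgeon or period, and the stated reading of participation. The surgeon restriction and the place of retrograde nails are lesser points that need clarifying.

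**What to change.** Before any comparison by arm, amend 2.0, 7.1 and 7.2 so that they agree.

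1. **One start event** for the time for two interlocks. The first shot is the practical candidate, because it alone has a recording instruction. Report time from readiness as secondary where it was recorded.
2. **One primary:** interlock time, jig versus freehand, at two-sided 5%. If the sponsor keeps radiation as primary, apply Holm across the two.
3. **One place for everything else:** accuracy, length of surgery and femur versus tibia each listed once, as secondary.
4. **Pooled or by bone:** state which. Pooling departs from the by-bone sizing that 7.2's numbers imply, so 7.2 should say so. A by-bone primary accepts the lower power shown above.
5. **Clarifications:** whether the more-than-5 count refers to experience before or during the trial, and whether retrograde nails count in the time primary. Make all patients by assigned method the main set, consistent with 4.0, and the restricted set a sensitivity analysis.

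The cost is wording, plus a check of which start times exist for patients already enrolled. On the figures above, a pooled primary needs no extra patients, although clustering has not been allowed for. The downsides are that outcomes moved to secondary can no longer be claimed as primary, that readiness times may be missing for patients already treated, and that a first-shot clock leaves out any set-up done before that shot.
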